## 8.4 Compliance in Investigational Medicinal Product Administration

The IMP is dispensed to the patient at each of the following visits:

- Visit 3 (Day 1)
- Visit 4 (Day 15)
- Visit 5 (Day 29)
- Visit 6 (Day 43)

- Visit 7 (Day 57)
- Visit 9 (Day 85)
- Visit 10 (Day113) (patients not entering the OLE)
- All OLE visits until the end of treatment

The patient or their caregiver will record the volume of solution taken on each treatment day in the diary.

Patients should return all IMP (used and unused) at each of visits 4, 5, 6, 7, 9, 10 and 11 during the blinded phase and at all OLE visits. The usage recorded in the diary and the usage projected in the dose calculator will be checked and any discrepancies discussed with the patient or their caregiver at the time of the visit and documented accordingly within the patient's source documents.

Records of IMP accountability will be maintained according to Section 5.3.4.

# 8.5 Access to Blinded Treatment Assignment (Blinded Phase and OLE Transition Only)

The identity of IMP assigned to patients will be held by the IVRS. The principal investigator (PI) at each center, or his/her designee, is responsible for ensuring that information on how to access the IVRS for an individual patient is available to the relevant staff in case of an emergency and unblinding is required. A patient's treatment assignment should only be unblinded when knowledge of the treatment is essential to make a decision on the medical management of the patient. Unblinding for any other reason will be considered a protocol deviation.

The investigator is encouraged to contact GW to discuss the rationale for unblinding prior to doing so. However, to prevent delays to the investigator or medical personnel responding to a potentially emergent situation, unblinding of study medication will not be dependent upon the investigator receiving approval from GW (i.e., the investigator will be able to obtain the code break information independent of contacting GW).

If the investigator does unblind, they must contact GW within one working day of the event and must document the time, date and reason(s) for unblinding on the patient's CRF.

# 9 STUDY PROCEDURES

A list of the required study procedures is provided in the subsections that follow; refer also to the Schedule of Assessments (APPENDIX 1). Assessments or tests that are not done and examinations that are not conducted must be reported as such in the CRFs.

The location of the source data for the following procedures will be documented, per center, in a signed 'Source Data Verification' plan; for further details see Section 16.2.

## 9.1 Study Procedures by Visit

Patients and their parent(s)/legal representative will be invited to take part in the study and will be issued with the patient information and informed consent/assent or the patient/parent(s)/legal representative information and informed consent. Following adequate time to discuss the study with the investigator, nurse, relatives or caregiver, as wished, patients/parent(s)/legal representatives who provide written informed consent/assent will be screened for entry into the study.

## 9.1.1 Blinded Phase

## 9.1.1.1 Visit 1 (Day -35, Screening)

Eligibility must be assessed according to the criteria specified in Section 6.

The following observations will be made at Visit 1: demographics, medical history (including seizure information since diagnosis, history of epilepsy-specific genetic testing and all prior AEDs taken), concomitant medications (including AEDs), physical examination (including height and body weight), ECG, vital signs, postural blood pressure and visit procedure-related AEs. With the patient/parent(s)/legal representative's consent, a further blood test will be carried out to determine the mutation status of *TSC1* and *TSC2*, if it is unknown.

The patient's documented history of TSC will be sent to the ESC to confirm seizure classification.

Clinical laboratory samples (blood and urine [where possible]), including pregnancy tests if appropriate (using both a serum sample and a urine dipstick), will be taken for hematology, biochemistry, urinalysis, and a urine/serum THC screen. Suicidality will be assessed in accordance with Section 9.2.12.8.

The investigator must record the patient's attendance at the visit and confirm the outcome of screening on the CRF.

## 9.1.1.2 Visit 2 (Day -28, Baseline)

This visit will occur 7 days after Visit 1. A visit window of  $\pm$ 7 days from the scheduled visit is permitted to ensure ESC confirmation of seizure classification, but it is preferred that the visit is performed on the scheduled visit day where possible.

Attendance of the patient is not required for this visit provided the primary caregiver is able to attend and that this caregiver (not the patient) will be responsible for seizure identification, IVRS use, and paper diary completion. However, it is preferred that the patient attend where possible.

The following observations will be made at Visit 2: review of concomitant medications (including AEDs), AEs and epilepsy-related hospitalizations.

Patients who satisfy all inclusion and none of the exclusion criteria specified in Section 6 will begin the 28 (+3)-day baseline period. The investigator will review and train the patient or their caregiver to identify the patient's expected seizure types. Patients or their caregivers will be issued with IVRS details and will be instructed on how to use it to record daily seizure information. Patients or their caregivers will also be given a paper diary to record usage of IMP, rescue medication, concomitant AEDs and AEs and will be instructed on how to do so.

## 9.1.1.3 Visit 3 (Day 1, Randomization)

This visit will occur 28 days after Visit 2. A visit window of +3 days from the scheduled visit date is permitted, but it is preferred that the visit is performed on the scheduled visit day where possible.

The following observations will be made at Visit 3: concomitant medications, (including AEDs), physical examination (including height and body weight), details of menstruation (for females), Tanner Staging (for patients aged 10–17 years [inclusive], or earlier if clinically indicated by onset of menarche or other signs of precocious puberty), ECG, vital signs, postural blood pressure, epilepsy-related hospitalizations, AEs and paper diary review. The ECG will be repeated four hours ( $\pm$ 30 minutes) after the first dose of IMP.

Clinical laboratory samples (blood and urine [where possible]), including pregnancy tests if appropriate (using both a serum sample and a urine dipstick), will be taken for hematology, biochemistry, urinalysis, and determination of serum IGF-1 levels (for

#### SPONSOR: GW RESEARCH LIMITED

patients less than 18 years of age). Provided that the risk/benefit outcome is favorable in the investigator's opinion, prior to the first daily dose of IMP, a blood sample will be taken for analysis of plasma concentrations of concomitant AEDs. PK samples (patients > 20 kg in weight only) will be taken in accordance with Section 9.2.9.1.

The investigator must assess the patient's daily number of seizures from the patient's IVRS data, record the patient's attendance at the visit, and confirm the outcome of the visit prior to randomization. Patients who have experienced at least eight seizures during the first 28 days of the baseline period, and who meet all of the other inclusion and none of the exclusion criteria specified in Section 6, will be eligible to continue in the study.

Eligible patients will then be randomized to receive GWP42003-P 25 mg/kg/day, GWP42003-P 50 mg/kg/day, placebo 25 mg/kg/day dose volume equivalent, or placebo 50 mg/kg/day dose volume equivalent at a 2:2:1:1 ratio.

Following randomization at Visit 3, patients will remain at the clinic where the following baseline assessments will be performed prior to the administration of study medication: QOLCE/QOLIE-31-P, Wechsler Tests, CBCL/ABCL, SCQ and the Vineland-II. Suicidality will be assessed in accordance with Section 9.2.12.8.

Patients/caregivers and investigators will be asked to write a brief description of their/the patient's overall condition and assess the average duration of seizure subtypes as a memory aid for the PGIC, SGIC/CGIC and SGIC-SD/CGIC-SD; these will be referred to at relevant, subsequent visits or withdrawal.

IMP will be dispensed for the following 2 weeks and patients or their caregivers will be provided with individual dosing schedules as described in Section 8.1 Each patient will then receive a titration regimen. The first dose of IMP will be administered in clinic.

Following Visit 3, during titration, safety telephone calls must be made every two days. If the call falls on a weekend, it is permitted to schedule the call for the Friday before or Monday after the weekend instead. A further call must be completed one week after the end of titration. During these calls, caregivers will be asked for information on AEs, epilepsy-related hospitalizations, concomitant medications and/or changes to medication. The investigator must retain oversight of safety telephone calls.

## 9.1.1.4 Visit 4 (Day 15)

This visit will occur 14 days after Visit 3 (randomization). A visit window of  $\pm 3$  days from the scheduled visit date is permitted, but it is preferred that the visit is performed on the scheduled visit day where possible.

The following observations will be made at Visit 4: concomitant medications, (including AEDs), physical examination (including height and body weight), ECG, vital signs, epilepsy-related hospitalizations and AEs.

Clinical laboratory samples (blood and urine [where possible]) will be taken for hematology, biochemistry and urinalysis.

Suicidality will be assessed in accordance with Section 9.2.12.8.

The investigator must assess adherence to the titration regimen by reviewing the patient's diary and IVRS data and record the patient's attendance at the visit.

All IMP (used and unused) will be collected and a check of the returned IMP against usage should be made. Patients will then receive a new treatment pack of the IMP.

Following Visit 4, during titration, safety telephone calls must be made every two days. If the call falls on a weekend, it is permitted to schedule the call for the Friday before or Monday after the weekend instead. During these calls, caregivers will be asked for information on AEs, epilepsy-related hospitalizations, concomitant medications and/or changes to medication. The investigator must retain oversight of safety telephone calls.

## 9.1.1.5 Visit 5 (Day 29)

This visit will occur 28 days after Visit 3. A visit window of  $\pm 3$  days from the scheduled visit date is permitted, but it is preferred that the visit is performed on the scheduled visit day where possible.

The following observations will be made at Visit 5: concomitant medications, (including AEDs), physical examination (including height and body weight), ECG, vital signs, postural BP, epilepsy-related hospitalizations and AEs.

Clinical laboratory samples (blood and urine [where possible]), including pregnancy tests if appropriate (using both a serum sample and a urine dipstick), will be taken for hematology, biochemistry and urinalysis. Provided that the risk/benefit outcome is favorable in the investigator's opinion, prior to the first daily dose of IMP, a blood sample will be taken for analysis of plasma concentrations of concomitant AEDs.

Suicidality will be assessed in accordance with Section 9.2.12.8.

The investigator must assess adherence to the titration regimen by reviewing the patient's diary and IVRS data and record the patient's attendance at the visit.

All IMP (used and unused) will be collected and a check of the returned IMP against usage should be made. Patients will then receive a new treatment pack of the IMP.

A safety telephone call must be made one week after the end of titration (Visit 5). During this call, caregivers will be asked for information on AEs, epilepsy-related hospitalizations, concomitant medications and/or changes to medication. The investigator must retain oversight of the safety telephone call.

#### 9.1.1.6 Visit 6 (Day 43)

This visit will occur 42 days after Visit 3 (randomization). A visit window of  $\pm 3$  days from the scheduled visit date is permitted, but it is preferred that the visit is performed on the scheduled visit day where possible.

The following observations will be made at Visit 6: concomitant medications, (including AEDs), physical examination (including height and body weight), ECG, vital signs, epilepsy-related hospitalizations and AEs.

Clinical laboratory samples (blood and urine [where possible]) will be taken for hematology, biochemistry and urinalysis. Suicidality will be assessed in accordance with Section 9.2.12.8.

The investigator must assess adherence to the dosing regimen by reviewing the patient's diary and IVRS data and record the patient's attendance at the visit.

All IMP (used and unused) will be collected and a check of the returned IMP against usage should be made. Patients will then receive new IMP.

#### 9.1.1.7 Visit 7 (Day 57)

This visit will occur 56 days after Visit 3 (randomization). A visit window of  $\pm 3$  days from the scheduled visit date is permitted, but it is preferred that the visit is performed on the scheduled visit day where possible.

The following observations will be made at Visit 7: concomitant medications (including AEDs), physical examination (including height and body weight), ECG, vital signs, epilepsy-related hospitalizations and AEs.

Clinical laboratory samples (blood and urine [where possible]), including pregnancy tests if appropriate (using both a serum sample and a urine dipstick), will be taken for hematology, biochemistry and urinalysis. Provided that the risk/benefit outcome is favorable in the investigator's opinion, prior to the first daily dose of IMP, a blood sample will be taken for analysis of plasma concentrations of concomitant AEDs.

Suicidality will be assessed in accordance with Section 9.2.12.8.

The investigator must assess adherence to the dosing regimen by reviewing the patient's diary and IVRS data and record the patient's attendance at the visit.

All IMP (used and unused) will be collected and a check of the returned IMP against usage should be made. Patients will then receive new IMP.

#### 9.1.1.8 Visit 8 (Day 71)

This visit will occur 70 days after Visit 3 (randomization). A visit window of  $\pm 3$  days from the scheduled visit date is permitted, but it is preferred that the visit is performed on the scheduled visit day where possible.

Visit 8 will be completed by telephone and will comprise a review of concomitant medications (including AEDs), epilepsy-related hospitalizations and AEs.

#### 9.1.1.9 Visit 9 (Day 85)

This visit will occur 84 days after Visit 3 (randomization). A visit window of  $\pm 3$  days from the scheduled visit date is permitted, but it is preferred that the visit is performed on the scheduled visit day where possible.

The following observations will be made at Visit 9: concomitant medications (including AEDs), physical examination (including height and body weight), ECG, vital signs, epilepsy-related hospitalizations and AEs.

Clinical laboratory samples (blood and urine [where possible]), including pregnancy tests if appropriate (using both a serum sample and a urine dipstick), will be taken for hematology, biochemistry and urinalysis. Provided that the risk/benefit outcome is favorable in the investigator's opinion, prior to the first daily dose of IMP, a blood sample will be taken for analysis of plasma concentrations of concomitant AEDs.

Suicidality will be assessed in accordance with Section 9.2.12.8.

The investigator must assess adherence to the dosing regimen by reviewing the patient's diary and IVRS data and record the patient's attendance at the visit.

All IMP (used and unused) will be collected and a check of the returned IMP against usage should be made. Patients will then receive new IMP.

#### 9.1.1.10 Visit 10 (Day 113, End of Treatment/Withdrawal Visit)

This visit will occur 112 days after Visit 3 (randomization) or earlier if the subject withdraws from the study. A visit window of  $\pm 3$  days from the scheduled visit date is permitted, but it is preferred that the visit is performed on the scheduled visit day where possible. Patients will be instructed to record the dosing time of their concomitant AEDs in the diary.

The following observations will be made at Visit 10/the Withdrawal visit: concomitant medications (including AEDs), physical examination (including height and body weight), Tanner Staging (for patients aged 10–17 years [inclusive], or earlier if clinically indicated by onset of menarche or other signs of precocious puberty), details of menstruation (for females), ECG, vital signs, epilepsy-related hospitalizations and AEs.

Clinical laboratory samples (blood and urine [where possible]), including pregnancy tests if appropriate (using both a serum sample and a urine dipstick), will be taken for hematology, biochemistry, urinalysis, and determination of serum IGF-1 levels (for patients less than 18 years of age) to be performed by the central laboratory. Provided that the risk/benefit outcome is favorable in the investigator's opinion, prior to the first daily dose of IMP, a blood sample will be taken for analysis of plasma concentrations of concomitant AEDs. PK samples (patients > 20 kg in weight only) will be taken in accordance with Section 9.2.9.1.

The following assessments will also be performed: QOLCE/QOLIE-31-P, PGIC, SGIC/CGIC, SGIC-SD/CGIC-SD, Wechsler Tests, CBCL/ABCL, SCQ and the Vineland-II. Suicidality will be assessed in accordance with Section 9.2.12.8.

The investigator must assess adherence to the dosing regimen by reviewing the patient's diary and IVRS data, record the patient's attendance at the visit and confirm the outcome of the visit.

All IMP (used and unused) will be collected and a check of the returned IMP against usage should be made.

For patients 12 years of age and older who do not enter the taper period, the trained investigator or study coordinator will complete the Study Medication Use and Behavior Survey as an interview with the patient/caregiver.

For patients who withdraw early, the IVRS will be contacted to confirm withdrawal from the study. Patients who withdraw should have their dose of IMP tapered gradually (10% each day) over a period of 10 days, beginning at the time the decision is made to discontinue. In some cases, tapering the dose of IMP may be inadvisable (e.g., continued dosing is not possible due to an AE). The decision on whether or not to taper IMP will be left to the investigator's clinical judgment. If tapering is undertaken, a 10-day supply of IMP (if required) and instructions for tapering the dose will be provided. Patients/caregivers should continue to complete the IVRS (see APPENDIX 4) and paper diary and should return for Visit 11 (the 'End of Taper Period' visit), if possible.

Patients who have completed all of the scheduled study visits will be offered the option of entering an OLE. Entry is to be on the same day as Visit 10 (Day 113).

Patients not entering the OLE at this visit will be given a 10-day supply of IMP (if required) and instructions for tapering the dose, during which time IVRS (see APPENDIX 4) and paper diary information will continue to be recorded.

#### 9.1.1.11 Visit 11 (Day 123, End of Taper)

This visit is required only for those patients who do not enter the OLE on the day of Visit 10 or for those who withdraw early and taper IMP. For patients who complete the study but opt not to enter the OLE, Visit 11 should occur 10 (+3) days after Visit 10 (i.e., on Day 123 [+3]). For patients who withdraw early and taper IMP, this visit should occur 10 (+3) days after the Withdrawal visit. For patients who begin to taper IMP but subsequently withdraw/do not complete the full taper period, this visit should occur on the final day of dosing or as soon as possible after this date.

The following observations will be made at Visit 11: concomitant medications (including AEDs), epilepsy-related hospitalizations and AEs, physical examination (including height and body weight), vital signs, ECG and clinical laboratory samples (blood and urine for hematology, biochemistry and urinalysis). Suicidality will be assessed in accordance with Section 9.2.12.8.

For patients 12 years of age and older, the trained investigator or study coordinator will complete the Study Medication Use and Behavior Survey as an interview with the patient/caregiver.

The investigator must assess adherence to the dosing regimen by reviewing the patient's diary and IVRS data and record the patient's attendance at the visit.

All IMP (used and unused) will be collected and a check of the returned IMP against usage should be made. The patient diaries will be collected.

Following Visit 11 (or date of final dosing) the IVRS seizure reporting diary should only be completed once more (see APPENDIX 4).

#### 9.1.1.12 Visit 12 (Day 151, Safety Follow-up)

This visit is required for patients who do not enter the OLE or who withdraw from the study early. This visit should occur four weeks after Visit 11 (+3 days), or date of final dosing, and can be conducted over the telephone. The following observations will be made at Visit 12: concomitant medications (including AEDs), epilepsy-related hospitalizations and AEs.

#### 9.1.2 Open-label Extension

Patients who successfully complete the blinded phase will be invited to participate in the OLE when they reach the End of Treatment visit (Visit 10) of the blinded phase. They will be issued with the OLE patient information and informed assent or the patient/parent(s)/legal representative information and informed consent (as applicable). Following adequate time to discuss the study with the investigator, nurse, relatives or caregiver, patients/parent(s)/legal representatives who provide written informed consent/assent at Visit B1 will be enrolled into the OLE. The OLE period will last for a maximum of 1 year; however, patients in the US and Poland may have the opportunity to continue in the OLE beyond this.

On-label use of mTOR inhibitors (for the treatment of seizures or tumors) and general anesthesia are permitted in the OLE phase of the trial.

#### 9.1.2.1 Visit B1 (Day 1)

Day 1 is regarded as the first day of IMP dosing. The following data collected at the 'End of Treatment' visit of the blinded phase will also be considered as Visit B1 data: vital signs, physical examination (including height and body weight), details of menstruation (for females), Tanner Staging (patients aged 10–17 [inclusive]), ECG, clinical laboratory samples (blood and urine for hematology, biochemistry, urinalysis, determination of serum IGF-1 levels [patients less than 18 years of age], and pregnancy tests [if appropriate]), IVRS and paper diary information from the blinded phase (including information regarding seizures, AEs, usage of rescue medication, concomitant AEDs, IMP dosing), epilepsy-related hospitalizations, AEs, concomitant medications and/or changes to medication, QOLCE/QOLIE-31-P, PGIC, SGIC/CGIC, SGIC-SD/CGIC-SD, Wechsler Tests, CBCL/ABCL, SCQ and the Vineland-II. Suicidality will be assessed in accordance with Section 9.2.12.8.

Patients will take their final dose of the blinded phase IMP in the morning of Visit B1, followed by collection of the blinded phase 'End of Treatment' assessments. Patients will be instructed to begin the Blinded Open-label transition, taking their first dose of Blinded Transition OLE IMP in the evening of Visit B1 (Day 1).

Patients or their caregivers will receive sufficient IMP for two weeks' home dosing together with a blinded transition phase. If an unacceptable AE develops at any time during transition, dosing should initially be suspended or amended, at the investigator's discretion, until the event has resolved or is well tolerated.

Patients or their caregivers will be given a paper diary to record information regarding AEs, IMP, usage of rescue medication, concomitant AEDs and IMP dosing. In addition, patients/caregivers will be instructed to complete a weekly seizure reporting diary until the Follow-up visit using the IVRS.

The investigator should review the laboratory results as soon as these become available. If the results raise any safety concerns, the investigator should consider whether it will be appropriate for the patient to continue to participate in the extension study, or if the patient should be withdrawn.

In order to complete the SGIC/CGIC, the patient/caregiver is to compare to the memory aid from the Baseline of the blinded phase. If the memory aid is not available from the Baseline of the blinded phase then the patient/caregiver should do this from memory, if possible, and complete a memory aid at Visit B1.

In order to complete the SGIC-SD/CGIC-SD, the patient/caregiver would have been asked to assess and note the average duration of the patient's seizures at the Baseline of the blinded phase as a memory aid for subsequent visits. If the memory aid is not available from the Baseline of the blinded phase then the patient/caregiver should do this from memory, if possible, and complete a memory aid at Visit B1.

Following Visit B1, during the blinded transition, safety telephone calls must be made every two days. If the call falls on a weekend, it is permitted to schedule the call for the Friday before or Monday after the weekend instead. During these calls, caregivers will be asked for information on AEs, epilepsy-related hospitalizations, concomitant medications and/or changes to medication. The investigator must retain oversight of safety telephone calls.

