#### 9.2.9.1 Pharmacokinetic Blood Sampling

The plasma concentration/time curves of CBD and its major metabolites will be assessed at Visits 3 and 10 for patients weighing more than 20 kg. Where appropriate, blood samples will be taken as follows:

- One sample pre-dose (i.e., prior to administration of IMP).
- One sample between 2 and 3 hours post-dose.
- One sample between 4 and 6 hours post-dose.
- One sample between 8 and 10 hours post-dose (patients 18 years and above only).

There must be a minimum period of at least two hours between each of the blood sampling time points. In the event of an AE that, in the opinion of the investigator, is related to a concomitant AED, additional blood samples may be collected.

For patients who undergo PK blood sampling, the patient/caregiver will record all meal times and the types of meals consumed by the patient during all PK testing days (Visits 3 and 10).

Analysis of all pharmacokinetic samples will be conducted at a central clinical laboratory. Sample volume requirements and processing procedures will also be detailed in a separate laboratory manual. The patient/caregiver must be advised that it may not be safe for them to undertake further blood tests within one month of any study-related blood draws and to inform the investigator if they suffered any blood loss during the one-month period leading up to a planned blood draw.

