#### 9.2.9.2 Determination of Plasma Concentrations of Concomitant Antiepileptic Drugs

Plasma concentrations of concomitant AEDs will be assessed at Visits 3, 5, 7, 9 and 10/ the Withdrawal visit (if possible) during the blinded phase and at Visits B2, B3, B4 and all subsequent Assessment Visits during the OLE. Samples will be collected for all patients provided that the risk/benefit outcome is favorable in the investigator's opinion. At each visit, blood samples will be taken prior to administration of IMP. Patients will be instructed to record the dosing time of their concomitant AEDs in the diary.

Additional blood samples may be taken for AED monitoring if there is a suspicion of changes in AED levels, with the aim to keep the AED plasma levels within the patient's therapeutic level. AED doses should be adjusted, as appropriate, following discussion with the GW medical monitor in order to maintain stable AED plasma concentrations.

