5.7.2 Pharmacokinetics of CBD and its Major Metabolites

Samples for PK analysis are taken on Visit 3 (first dose, Day 1) and Visit 10 (last maintenance dose of the blinded phase, Day 113) for patients weighing more than 20 kg. For patients recruited under Protocol Version 2, PK samples were taken at the following time-points:

- Prior to administration of IMP, ≤ 0.0 hours pre-dose on Visit 3 or C_{trough} at steady state (Visit 10).
- ≥ 4.0 hours to ≤ 5.0 hours.
- ≥ 6.0 hours to ≤ 7.0 hours.
- ≥ 8.0 hours to ≤ 10.0 hours, for patients 18 years or older.

Patients recruited under Protocol Version 3 onwards, PK samples were taken at the following time-points:

- Prior to administration of IMP, ≤ 0.0 hours pre-dose on Visit 3 or C_{trough} at steady state (Visit 10).
- ≥ 2.0 hours to ≤ 3.0 hours.
- ≥ 4.0 hours to ≤ 6.0 hours.
- ≥ 8.0 hours to ≤ 10.0 hours, for patients 18 years or older.

The nominal mid-point time of 0, 2.5, 4.5, 5, 6.5 and 9 hours will be used for summaries of plasma concentrations. Plasma concentrations and PK parameters will be summarized showing the number of non-missing values (n), arithmetic mean, standard deviation, coefficient of variation (%), median, minimum and maximum. Where samples are reported as BLQ, a value of zero will be used in the summaries. Summary statistics will be presented to 3 significant figures.

Where data allow, the PK parameter AUC_{0-t} will be derived at each visit by the PK vendor. A dose-normalized AUC_{0-t} will be calculated as AUC_{0-t} divided by the randomized dose per administration (12.5 or 25 mg/kg). This will include Visit 3, for consistency, where the first dose of IMP will be 2.5 mg/kg.

Plasma concentrations of CBD and its major metabolites 7-hydroxy-CBD (7-OH-CBD) and 7-carboxy-CBD (7-COOH-CBD) will be summarized by nominal mid-point time, visit and GWP42003-P arm. In addition, a dot plot of plasma concentrations for each patient, by nominal mid-point time will be created for each visit and GWP42003-P arm. The arithmetic mean will be highlighted on the plot. Additionally, a line plot of the arithmetic mean plasma concentration will be created with standard error bars by nominal mid-point time for each visit and GWP42003-P arm. These plots will be presented both a linear and semi-logarithmic scale for plasma concentration.

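### For OLE entrants, Protocol 9.1.2.1 puts the Day 113 morning dose before the End of Treatment assessments, but the sampling sections require the Visit 10 trough and AED samples before that dose

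*Protocol*

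**What the plan says.** **One day, two visit numbers.** Protocol 9.1.1.10 says of OLE entry: "Entry is to be on the same day as Visit 10 (Day 113"). The End of Treatment visit and Visit B1 therefore coincide for every OLE entrant.

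**Order in Protocol 9.1.2.1.** "Patients will take their final dose of the blinded phase IMP in the morning of Visit B1, followed by collection of the blinded phase" (that is, what comes after the dose is the set of End of Treatment assessments). The next dose is the first transition dose, that evening.

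**Order in the sampling sections.**
- Protocol 9.1.1.10, AED levels at Visit 10: "prior to the first daily dose of IMP, a blood sample will be taken for analysis of plasma concentrations of concomitant AEDs".
- Protocol 9.2.9.2, the same rule for all AED visits: "At each visit, blood samples will be taken prior to administration of IMP". The synopsis also lists Visit 10 as pre-IMP.
- Protocol 9.1.1.10, PK at Visit 10: "PK samples (patients > 20 kg in weight only) will be taken in accordance with Section 9.2.9.1". That section begins its schedule with "One sample pre-dose (i.e., prior to administration of IMP"), at Visits 3 and 10.

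**Use in the SAP.** SAP 5.7.2: "Samples for PK analysis are taken on Visit 3 (first dose, Day 1) and Visit 10 (last maintenance dose of the blinded phase, Day 113"). The first time-point has a window of 0.0 hours or earlier and is described as "pre-dose on Visit 3 or C_{trough} at steady state (Visit 10"). Its nominal time is 0. SAP 5.7.3 tabulates AED concentrations by arm at Visits 3, 5, 7, 9 and 10.

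**The concern.** IMP is taken morning and evening, so the morning dose is the first daily dose. A sample cannot both precede that dose and belong to a set of assessments that follows it. Section 9.1.2.1 is the part of the protocol written for patients moving into the OLE, so a site enrolling one has reason to follow it.

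Visit 10 is the only multiple-dose PK visit; Visit 3 covers the first dose. If the first Visit 10 sample is drawn after the dose, it is not a trough, and the Visit 10 AUC0-t has no valid starting point. The AED sample would also stand in a different relation to IMP dosing from those at Visits 3, 5, 7 and 9, beside which it is tabulated. Nothing can be recovered later, because the evening dose already belongs to the transition.

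**Working it through.** No figure in the plan is at issue, so the check sets the passages side by side.

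**Step 1: the two orders on Day 113 (t = 0 is the final blinded morning dose).**

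| Event | Protocol 9.1.2.1 | Synopsis, Protocol 9.1.1.10, 9.2.9.1, 9.2.9.2 |
|---|---|---|
| AED sample | t > 0, as an End of Treatment assessment | t ≤ 0 |
| First PK sample | t > 0, as an End of Treatment assessment | t ≤ 0 |
| PK at 2–3 h, 4–6 h, and 8–10 h (18 years and above) | t > 0 | t > 0 |

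The later PK samples fit both orders. The first PK sample and the AED sample fit only the second.

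**Step 2: does any text resolve it?**
- Section 9.1.1.3 says the first dose at Visit 3 is given in clinic. No matching sentence exists for Visit 10 or B1, and none says that the morning dose waits for the samples.
- Section 9.1.2.1 lists the End of Treatment data that also count as B1 data, and this list omits PK and AED levels. Its dosing sentence, however, refers to the End of Treatment assessments without exception, and Appendix 1 schedules both samples at Visit 10.
- The OLE part of Appendix 1 has no AED mark at B1 and no PK row, so B1 offers no separate collection.
- Sections 9.1.1.10 and 9.2.9.2 ask for AED dosing times, and 9.2.9.1 asks for meal times on PK days. None of them asks for the IMP dose time, although the SAP windows presuppose it.

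**Step 3: what the SAP would do with such a sample.**
- It fails the window of 0.0 hours or earlier.
- Under the schedule used from Protocol Version 3, a draw before 2 h fits no window. A draw at 2–3 h falls in the 2.5 h window.
- SAP 5.7.2 allows individual time-points to be excluded and gives criteria such as vomiting, missed doses and dose reduction. A pre-dose sample taken after the dose is not named.
- The SAP does not say whether AUC0-t uses nominal or actual times. With nominal times, the sample would be misplaced at zero. With actual times, the zero point would be missing.

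**Step 4: ceiling on the number affected.**
- Randomization of 210 at 2:2:1:1 gives 210 × 4/6 = 140 active and 210 × 2/6 = 70 placebo.
- The OLE entry rate is not in the documents. Assume 70–95%.
- PK is summarized for the GWP42003-P arms only: 140 × 0.70 = 98 and 140 × 0.95 = 133. The limit to patients over 20 kg lowers this by an unknown amount, as enrolment starts at age one.
- AED sampling covers all arms: 210 × 0.70 = 147 and 210 × 0.95 = 199.5, less those not sampled on risk/benefit grounds.
- One AED time-point of five (Visits 3, 5, 7, 9, 10) is involved.

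These are ceilings. They would be reached only if every site followed 9.1.2.1 literally.

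**The case against.** The strongest reply is that four places say pre-dose and one sentence implies otherwise. A sensible site would draw the samples, let the patient take the dose, and then do the rest. Section 9.1.2.1 does not say that the dose is taken at home, and its list of shared data leaves out PK and AED levels. This stands as a limit on the effect. It does not remove the conflict, because no text exempts the two samples from the stated order.

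The SAP also helps. Its first window already excludes a post-dose sample by definition, AUC0-t is derived only where data allow, and its exclusion list is open-ended. This stands in part: the definition is right, but no rule says what happens to a sample labelled pre-dose that fails it.

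A reader might infer three stronger points that the documents do not support:
- **That the later PK windows shift.** They are defined relative to the dose and do not move.
- **That a false drug interaction would appear.** The AED rule is pre-IMP, not pre-AED. Section 8.1.1 permits IMP with other medicines but does not require it, AED dosing times go in the diary, and the summaries are descriptive. Placebo entrants share the same Day 113 instructions, so a timing artefact would tend to appear in that arm too. Within-arm comparison of Visit 10 with earlier visits is less protected.
- **That 147–200 patients bound the PK problem.** That range includes placebo patients, who are not in the CBD summaries.

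Finally, SAP 5.2.3 records blinded data review meetings on 22 and 25 March 2019, and Protocol Version 8 is dated 23 April 2019. Blinded dosing was probably complete by then (an inference), so rewording the protocol may change few samples. The SAP rule would still work.

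**Conclusion.** The conflict is real and lies in the text. A reader might conclude that every OLE entrant's Visit 10 trough and AED sample are post-dose. The documents do not support that: it happens only where a site follows 9.1.2.1 literally, and sites following the sampling sections are unaffected. The likely result is inconsistency between sites, with true and false troughs under one label and some AUC0-t values lacking a valid time zero.

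The number affected cannot be computed, since the documents give no OLE entry rate, weight distribution or site practice. For PK it is at most the active-arm entrants over 20 kg: 98–133 before the weight limit, on the assumed 70–95% entry. The size of the error in any one concentration cannot be stated either.

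Only exploratory PK and AED summaries are touched. The primary and key secondary analyses are not. The correction is worth making because it is cheap and Visit 10 is the trial's only steady-state PK visit.

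**What to change.** **Protocol.** Reconcile 9.1.2.1 with the synopsis, 9.1.1.10, 9.2.9.1 and 9.2.9.2 so that one order of sampling and dosing applies on Day 113 for OLE entrants. Require that day's IMP dose time and the sample times to be recorded. No dose or dosing rule is proposed here; how the order is settled is for the sponsor.

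**SAP 5.7.2.** Add that any Visit 10 sample labelled pre-dose but timed after that day's IMP dose is excluded from the pre-dose and trough summaries and is not used as time zero for AUC0-t. It stays in the listings with the reason.

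**SAP 5.7.3.** Flag Visit 10 AED samples taken after that day's IMP dose.

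**Cost.** One reconciled sentence and a recording requirement in the protocol, and one sentence in each of two SAP sections. If the Day 113 visits are already complete, the SAP rules can still be applied wherever dose and sample times were captured.
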